4.2.2 Definition of Baseline and Visit Time Windows

This observational study covers three documentation periods, see Figure 1. An overview of data to be collected throughout the study is summarized in Table 1.

Table 1 - Data Documentation Schedule

Assessment/ Procedure (only available data to be collected; no diagnostic or monitoring procedures to be applied to the patients apart from those of routine clinical practice)	Baseline	Treatment Period			Post-treatment (PT) Period		
		On-treatment visits	Mid treatment visit for pts receiving 24 weeks of therapy	EoT ^b	Early PT visit	SVR 12 visit	SVR 24 visit
Informed Consent	X ^a						
Demographic information	X						
IL28B	X						
Relevant CHC disease characteristics	X						
Liver fibrosis stage	X						
CHC treatment history	X						
HCV genotype and subtype	X						
HCV RNA samples	X	X	X	X	X	X	X
Clinical chemistry and hematology	X	X	X	X	X	X	X
ABBVIE REGIMEN initiation documentation	X						
ABBVIE REGIMEN adherence		X	X	X			
Concomitant medication	X	X	X	X			
Relevant medical history, co-morbidities	X						
sAE, AE and pregnancy reporting	X	X	X	X	X ^c	X ^d	X ^d
For patients receiving RBV: Evidence, in accordance with local label, that female patient or female partner of male patient is not pregnant	X						
Patient questionnaires – WPAI, EQ5D-5L	X			X		X	X
Health care resource utilization	X	X	X	X			

Abbreviations: EoT = End of Treatment (at Week 12 or 24 or at premature discontinuation),

PT = Post-Treatment

a Written informed consent must be obtained before any data documentation in the eCRF

b Patients who prematurely discontinue should return to the site to document EoT data

c Tolerability documentation until PT week 4

d Pregnancy reporting for patients treated with DAA +/- RBV

In accordance with the non-interventional nature of the study all HCV RNA measurements will be performed at the sole discretion of the physician and all HCV RNA measurements have to be entered into the eCRF. All recorded HCV RNA values will be assigned to appropriate time points (baseline, on-treatment visits, EoT visit, post-treatment visits) as follows:

Table 2 - Analysis Time Windows for HCV RNA

Phase	Time point	Time Window
Pre-Treatment	Baseline	Last value prior to start of study treatment (i.e. \leq study day 1)
On-treatment		Study day during treatment period ^{^#} (Study day 1 = first treatment day)
Treatment Week	4 (RVR*)	15 - 42 [^]
EoT	Actual EoT	Study day of last dose# (28 days prior to last dose - 7 days post last dose)
Post Treatment	12 weeks (SVR 12 window)	\geq 70-126 days post last dose
	24 weeks (SVR24 window)	127-210 days post last dose
	48 weeks\$	> 210 days post last dose

[^]values must also be \leq 7 days post last dose

\geq study day 2

*RVR = rapid virological response

\$ Please note that this time window is not specified in the study protocol, but added to consider possible relapse after day 210 in the analysis of the relapse rate. Analyses of SVR48 are not planned.

All reported safety laboratory test results will be assigned to one of the time points using the time windows specified in the table below.

Table 3 - Analysis Time Windows for Safety Laboratory Data

Phase	Time point	Time Window
Pre-Treatment	Baseline	Last value prior to start of study treatment (i.e. \leq study day 1)
Treatment Weeks	4 (day 29)	Study day during treatment period (Study day 1 = first treatment day)
	8 (day 57)	15 – 42 [^]
	12 (day 85)	43 – 70 [^]
	16 (day 113)	71 – 98 [^]
EoT	Actual EoT	Study day of last dose# (28 days prior to last dose - 7 days post last dose)
Post Treatment	4 weeks (28 days post last dose)	8– 56 post last dose
	12 weeks (84 days post last dose)	57 – 126 days post last dose
	24 weeks (168 days post last dose)	127 – 252 days post last dose
	48 weeks (336 days post last dose)\$	253 – 420 days post last dose

[^]values must also be \leq 7 days post last dose

\geq study day 2

\$ Please note that this time window is not specified in the study protocol, but added to consider possible reported values.

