The ABBVIE REGIMEN has been studied with and without RBV in over 2,300 patients in Phase III trials across a variety of patient populations including those with compensated cirrhosis. Based on Phase III data, the ABBVIE REGIMEN, with or without RBV, was well tolerated with a low discontinuation rate. Adverse events (AEs) were typically mild, and many of the AEs and laboratory abnormalities reported were attributable to the presence of RBV. However, these AEs were much milder than observed when RBV was given in combination with interferon. Transient, asymptomatic serum alanine aminotransferase (ALT) elevations were observed at a low rate, were not associated with hepatic dysfunction and generally resolved with ongoing treatment. A disproportionate number of the cases were in women on concurrent ethinyl estradiol-containing therapy (i.e., contraceptives or hormone replacement) and discontinuation of the hormonal therapy with continuation or brief interruption of the ABBVIE REGIMEN led to resolution in serum ALT elevation. Transient elevations in serum bilirubin (predominantly indirect) were observed in subjects receiving the ABBVIE REGIMEN with RBV, related to the inhibition of the bilirubin transporters, organic anion-transporting polypeptides (OATPs) 1B1/1B3, by paritaprevir and RBV-induced hemolysis. Bilirubin elevations occurred after initiation of treatment, peaked by study Week 1, and generally resolved with ongoing therapy.

---

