## 9.2.2 Study Duration

This is a prospective, observational study. The inclusion period will be approximately 12 months and the observational period of the study will be from baseline visit until 24 weeks post-treatment.

The observational period for patients receiving 12 weeks of ABBVIE REGIMEN will be max. 36 weeks (12 weeks treatment and 24 weeks post-treatment observation) and for patients receiving 24 weeks of ABBVIE REGIMEN the observational period will be max. 48 weeks (24 weeks treatment and 24 weeks post-treatment observation).

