##### Confidential Information

No use or disclose outside AbbVie is permitted without prior written authorization from AbbVie

The Netherlands v 1.4 (26 March 2018). Protocol based on AbbVie shell protocol version 3.0 (22 April 2015) Page 27 of 65

The following will be documented if available:

- Laboratory data

Key clinical chemistry

- ALT
- AST
- $\gamma$ -GT
- Total bilirubin
- Creatinine

Remarks

- including ULN
- including ULN,  
APRI and FIB-4 will be calculated
- creatinine clearance will be calculated

Key hematology

- Hb
- Platelets

Virology

- HCV RNA

quantitative/ qualitative HCV RNA PCR test, see 9.4.1.4

HIV-infected patients only

- CD 4 count
- HIV RNA

most recent assessment  
in copies/mL

- Concomitant medication, see 9.4.1.5
- Adherence to ABBVIE REGIMEN  $\pm$  RBV as established by interviewing the patient during regular visits
- Tolerability (sAEs and AEs, see 11.1.5) and pregnancies (see 11.1.6)
- Patient questionnaires see 9.4.1.6
- Treatment related health care resource utilization

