**Table 4 - Analysis Time Windows**

Phase	Time point	Time Window
Pre-Treatment	Baseline	Last value prior to start of study treatment (i.e. $\leq$ study day 1)
Treatment Weeks	4 (day 29)	Study day during treatment period (Study day 1 = first treatment day)
	8 (day 57)	15 - 42
	12 (day 85)	43 - 70
	16 (day 113)	71 - 98
EoT	Actual EoT	99 - 126
		Study day of last dose (28 days prior to EoT - 7 days post EoT)
Post Treatment	4 weeks (28 days post EoT)	8 – 56 post EoT
	12 weeks (84 days post EoT)	57 – 126 post EoT
	24 weeks (168 days post EoT)	127 – 252 post EoT

Mean changes from baseline to each post-baseline visit will be summarized descriptively.

---

Confidential Information

Laboratory data values collected during the treatment period will be categorized as low, normal, or high based on reference ranges used in this study. The number and percent of patients who experience post-baseline shifts during treatment in clinical laboratory values from low/normal to high and high/normal to low based on the reference range will be summarized.

Additional details of the analyses of clinical laboratory data will be specified in the SAP.

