4.2.8.4 Laboratory Data

All reported clinical laboratory test results will be assigned to one of the time points using the time windows specified in the Table 3. All will be performed for the SP by treatment regimen and cirrhosis status.

Changes from baseline to each post-baseline visit will be summarized descriptively (N, mean, SD, median, minimum, maximum). A summary table will show laboratory hematology. In another table, information about clinical chemistry will be summarized.

In a further table CD4 and HIV-RNA are displayed for patients with HIV only by visit.

Instead of the shift tables mentioned in the study protocol, the number and percentage of subjects with post-baseline values until EoT meeting the specified criteria for Potentially Clinically Significant (PCS) laboratory values (defined in Table 2) will be summarized. A post-baseline value must be more extreme than the baseline value to be considered a PCS finding.

Table 9 Criteria for PCS laboratory values

Laboratory data	Very Low	Very High
Laboratory hematology		
Hemoglobin [g/L]	<80	
Platelets [10^9 /L]	<50	
Laboratory clinical chemistry		
ALT		>5 x ULN and >= 2 x baseline
AST		>5 x ULN and >= 2 x baseline
Creatinine [$\mu\text{mol}/\text{L}$]		>132.605
Creatinine clearance [mL/min]***	<50	

*** estimated by Cockcroft-Gault-Formula (see above)

Additionally, for hemoglobin and creatinine clearance, the number and percentage of subjects with a maximum Common Terminology Criteria for Adverse Events (CTCAE) Grade of 0, 1, 2, 3, or 4 (see definitions in Table 10) at any post-baseline visit (regardless of the baseline value) through the end of treatment (i.e., Final Treatment Value) will be summarized. For the liver function tests (LFTs) of ALT and AST, the number and percentage of subjects in with a maximum CTCAE Grade of 0, 1, 2, 3, or 4 (see definitions in Table 10) at any post-nadir visit through the end of treatment (i.e., Final Treatment Value) will be summarized. Note, for these analyses, the nadir is used for reference (including baseline).

Table 10 Definition of CTCAE Grades 0-4

Laboratory data	Grade 0	Grade 1	Grade 2	Grade 3	Grade 4
ALT	<=ULN	>ULN – 3 x ULN	> 3 – 5 x ULN	> 5 – 20 x ULN	> 20 x ULN
AST	<=ULN	>ULN – 3 x ULN	> 3 – 5 x ULN	> 5 – 20 x ULN	> 20 x ULN
Hemoglobin Decreased [g/L]	>=130	<130 – 100	< 100 - 80	< 80 - 65	< 65
Creatinine Clearance [mL/min]	>= 75	< 75 - 60	< 60 - 30	< 30 – 15	< 15

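### The laboratory time windows leave days 2–14 (and a late stretch of 24-week courses) without a time point, so the by-visit tables omit any week 1–2 total bilirubin values

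*SAP*

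**What the plan says.** SAP 4.2.2 gives a rule with no exceptions: "All reported safety laboratory test results will be assigned to one of the time points using the time windows specified in the table below". Protocol 9.7.4 and SAP 4.2.8.4 state the same rule for clinical laboratory results.

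Table 3 of the SAP and Table 4 of the protocol share one structure:

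- Baseline is the "Last value prior to start of study treatment", that is, study day 1 or earlier.
- On-treatment time points are weeks 4, 8, 12 and 16, with ranges that start at day 15.
- EoT is "28 days prior to last dose - 7 days post last dose" in the SAP and "28 days prior to EoT - 7 days post EoT" in the protocol.
- Post-treatment windows start 8 days after the last dose.

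SAP 4.2.8.4 then builds its main laboratory tables on these windows: "Changes from baseline to each post-baseline visit will be summarized descriptively". The same section replaces the protocol's low/normal/high shift tables with a PCS summary (Table 9) and adds worst CTCAE grades (Table 10).

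Protocol 7.1 describes the time course of one known laboratory effect, in patients receiving the regimen with ribavirin: "Bilirubin elevations occurred after initiation of treatment, peaked by study Week 1, and generally resolved with ongoing therapy". "Total bilirubin" is among the on-treatment laboratory variables in Protocol 9.4.1.2, recorded if available.

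**The concern.** The assignment rule and the table contradict each other. A result from day 8 is a reported safety laboratory result, yet Table 3 has no row for it in a patient who completes treatment.

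For most analytes another output picks the value up. For total bilirubin none of the laboratory tables does, and weeks 1–2 include the time at which the protocol says the elevations peaked. The protocol's shift tables covered values from the whole treatment period and, as worded, did not depend on visit windows. Once the SAP replaced them with criteria that omit bilirubin, that route closed.

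Tolerability is a secondary objective, and the SAP's safety tables separate patients with and without ribavirin, which is the contrast Protocol 7.1 draws for bilirubin. An early bilirubin value that was collected would not enter that comparison.

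**Working it through.** **Inputs**

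- Baseline: day 1 or earlier (SAP Table 3, Protocol Table 4).
- Week 4: days 15–42. Week 8: 43–70. Week 12: 71–98 (both tables).
- Week 16: days 99–126, from Protocol Table 4. In the copy of the SAP reviewed, the rows of Table 3 are shifted and this range is missing. That is taken as conversion damage, not as an error in the plan.
- EoT: from L − 28 to L + 7, and not before study day 2, where L is the study day of the last dose (SAP Table 3).
- Course length: 12 weeks = 84 days or 24 weeks = 168 days (Protocol 9.2.2, for example "24 weeks of ABBVIE REGIMEN the observational period will be max. 48 weeks (24 weeks treatment and 24 weeks post-treatment observation").

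**Check of the stated windows.** The midpoints of the four on-treatment ranges are 28.5, 56.5, 84.5 and 112.5, against nominal days 29, 57, 85 and 113. The ranges run without a break from day 15 to day 126, so each range fits its label and the four leave no gap between them.

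**First gap.** Days 2–14 can be assigned only if the EoT window reaches back into them.

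- All of days 2–14 are unassigned when L − 28 ≥ 15, so L ≥ 43.
- Day 7 falls in the EoT window when L − 28 ≤ 7, so L ≤ 35.
- There is no gap when L − 28 ≤ 2, so L ≤ 30.

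**Second gap.** Days from 127 to L − 29 are unassigned when L − 29 ≥ 127, so L ≥ 156.

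| Last dose (day) | EoT window | Unassigned on-treatment days |
|---|---|---|
| 84 | 56–91 | 2–14 |
| 155 | 127–162 | 2–14 |
| 160 | 132–167 | 2–14, 127–131 |
| 168 | 140–175 | 2–14, 127–139 |
| 175 | 147–182 | 2–14, 127–146 |

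**Size in days.** Days 2–14 are 14 − 2 + 1 = 13 days, and 13/84 ≈ 15%. Days 127–139 are 139 − 127 + 1 = 13 days, and (13 + 13)/168 ≈ 15%. These are shares of the treatment calendar, not of samples.

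**Which analytes lose their only laboratory output.** The on-treatment variables in Protocol 9.4.1.2, set against the SAP's non-visit summaries:

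| Analyte | PCS (Table 9) | CTCAE (Table 10) |
|---|---|---|
| ALT, AST | yes | yes |
| Hemoglobin | yes | yes |
| Platelets | yes | no |
| Creatinine | yes | no |
| Creatinine clearance | yes | yes |
| Total bilirubin | no | no |
| γ-GT | no | no |

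The PCS summary takes values after baseline up to EoT and is not worded by window, so early values of the analytes in Table 9 still count there. Among routine chemistry and hematology variables, only total bilirubin and γ-GT have no other laboratory summary.

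**The case against.** The strongest case against the point is that no loss of data is shown. Laboratory values are recorded only if routine practice produced them. Patients may enrol up to four weeks into treatment, and a 12-week course has only two interim collection windows. Figure 1, which places those windows, was not readable in the copy reviewed. Whether any day 2–14 bilirubin values exist among 50–55 patients is therefore unknown. This stands. It limits the size of the point but does not reconcile the rule with the table.

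Four stronger readings are tempting, and the documents do not support them.

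- *Early safety data are discarded altogether.* They are not. Early ALT, AST, hemoglobin, platelet and creatinine values remain in the PCS summary. A bilirubin rise can be reported as an adverse event, since the protocol's definition includes abnormal laboratory findings. Jaundice and dark urine are tabulated as treated symptoms.
- *The by-visit tables will understate the bilirubin effect because they show only its resolved phase.* Protocol 7.1 gives no time to resolution, so values from day 15 may still be raised. Columns labelled week 4 and later do not claim to estimate a week-1 peak.
- *A week-1 value can never appear.* In a patient whose last dose is by about day 35, it falls in the EoT column.
- *Days 127–139 are a fixed hole.* They depend on the protocol's 99–126 range and a last dose exactly on day 168. The documents tie no specific safety concern to those days, and the schedule has no week-20 visit.

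Adverse-event reporting is only a partial substitute. It depends on someone judging the value reportable, and a week-1 chart value may predate consent.

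**Conclusion.** The concern holds in a limited form. The statement that every safety laboratory result is assigned is untrue for days 2–14 in all patients treated to day 43 or later. It is also untrue from day 127 to the start of the EoT window in courses whose last dose is on day 156 or later. The first result follows from both tables as they stand. The second assumes that the SAP's week-16 range matches the protocol's.

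The practical consequence is confined mainly to total bilirubin and γ-GT, and for bilirubin mainly to the ribavirin strata, where the protocol describes the elevations. Any week 1–2 bilirubin values would be missing from the by-visit change tables and would enter no other planned laboratory table. How many values that is cannot be derived from the documents. The primary endpoint is unaffected. The point is a modest one, worth correcting because the correction is cheap and makes the plan's own rule true.

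**What to change.** 1. Add a days 2–14 row to SAP Table 3, with the same limit of 7 days after the last dose that the other on-treatment rows carry.
2. For 24-week courses, add a row from day 127 to the day before the EoT window opens (L − 29). It is empty when the last dose is on day 155 or earlier.
3. Add a summary of the maximum on-treatment change from baseline in total bilirubin, over all post-baseline values to EoT regardless of window, by the existing safety groups. This row shows an early peak whatever the sampling pattern. A matching row for ALT and AST is optional, because the PCS and CTCAE summaries largely cover them.

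With rows 1 and 2 in place, every day from day 2 to the end of the EoT window has a time point: for L = 168, days 2–14, 15–126, 127–139 and 140–175. In early stoppers the new first row will overlap the EoT window, as the existing rows already do.

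The change can be made in the SAP, which already adds post-treatment windows that the protocol lacks; Protocol Table 4 can be aligned if it is next revised. The cost is a few extra table rows, possibly sparse, and no new data collection.

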4.2.3 Handling of missing data

No data will be imputed for any effectiveness or safety analyses except for the analyses of the HCV RNA endpoints and certain PRO endpoints. The discussion of missing data imputation for the PRO endpoints is included in section 4.2.7.2.2.

HCV RNA values will be selected for an RVR, EOTR and SVR analysis based on visit windows as defined in Table 2. When there is no HCV RNA value in a visit window based on defined visit windows, the closest values before and after the window, regardless of the value chosen for the subsequent and preceding window, will be used for the flanking imputation described below. For

analysis of RVR, EOT and SVR, if a subject has a missing HCV RNA value at a post-Day 1 visit but with undetectable or unquantifiable (LLoD or LLoQ \leq 50 IU/mL) HCV RNA levels at both the preceding value and succeeding value, the HCV RNA level will be considered undetectable or unquantifiable, respectively, at this visit for this subject. In addition, if a subject has an unquantifiable HCV RNA level at the preceding value and an undetectable HCV RNA level at the succeeding value, or vice versa, the HCV RNA level will be imputed as unquantifiable at this visit for this subject.

For analyses of RVR, subjects still missing a value for the visit after flanking imputation will be considered as a failure. For EoTR and SVR analysis, if there is no value in the appropriate window after flanking imputation but there is an HCV RNA value after the window, then it will be imputed into the EoTR or SVR window respectively. Subsequent to this flanking and backward imputation, if the HCV RNA value remains missing at a specific time point, then the subject will be considered as virological failure at this time point (i.e., not undetectable or unquantifiable).

If a subject starts another treatment for HCV, then all HCV RNA values for this subject measured on or after the start date of the new HCV treatment will be excluded from analyses. The subject will be considered a failure for summaries of viral response at all time points after the start of the new HCV treatment.

Due to the non-interventional nature of this study several different methods for determination of the HCV RNA value can be applied. For the purpose of the statistical analysis, a HCV RNA measurement is considered <50 IU/mL,

- if a PCR test was used
- and the test result is undetectable and the LLoD of the test is \leq 50 IU/mL or the test result is unquantifiable (i.e. detected but below LLoQ) and the LLoQ is \leq 50 IU/mL.

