4.2.7.2 Secondary Variables

4.2.7.2.1 Secondary Effectiveness Variables

Response

For the other response rates (i.e. SVR24, EoT response rate, relapse rate, viral breakthrough), the simple percentage of patients and a two-sided 95% confidence interval (CI) of the percentage will be computed (based on the Wilson's score method) as well. The EoT response rates will be reported for CP and the SVR24 rates will be reported for the respective CPSFU, stratified by genotype and cirrhosis status and overall. The relapse rates will be estimated stratified by SVR window (i.e. during SVR12 window=relapse₁₂, during SVR24 window=relapse₂₄, after SVR24

window=relapse_{late}) and stratified by genotype and cirrhosis status and overall in patients of the CP with EoT response who fulfilled the following criteria:

- completed treatment as defined previously,
- had at least one HCV RNA measurement ≥ 70 days post-treatment or was a treatment failure between EoT and 70 days post-treatment.

Viral breakthrough rates [defined as at least one documented HCV RNA <50 IU/mL followed by HCV RNA ≥ 50 IU/mL during treatment] will be estimated overall and stratified by genotype and cirrhosis status in all patients of the CP, who have at least one undetectable or unquantifiable, on-treatment HCV RNA measurement and at least one on-treatment or EoT measurement thereafter.

Non-Response

In another table, the numbers and the percentages of the SVR12 non-responder categories and responder will be summarized for CP patients, overall and stratified by genotype and cirrhosis status. The following SVR12 non-response categories will be considered:

- On-treatment virologic failure (breakthrough [defined as at least one documented HCV RNA <50 IU/mL followed by HCV RNA ≥ 50 IU/mL during treatment] or failure to suppress [each measured on-treatment HCV RNA value ≥ 50 IU/mL])
- Relapse (defined as HCV RNA <50 IU/mL at EoT followed by HCV RNA ≥ 50 IU/mL post-treatment and completed treatment as defined previously)
- Death and none of the above
- Premature study drug discontinuation with no on-treatment virologic failure and none of the above
- Insufficient virological response, other than those mentioned above (patients for whom insufficient virological response was reported, or who had HCV RNA ≥ 50 IU/mL post EoT) and none of the above
- Missing SVR12 data and/or none of the above criteria

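### The SAP does not say whether the relapse rate uses observed or imputed end-of-treatment status, and it silently drops the protocol's last on-treatment fallback from the relapse category

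*SAP*

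**What the plan says.** Below, negative means HCV RNA counted as below 50 IU/mL and positive means 50 IU/mL or above.

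**Relapse rate.** SAP 4.2.7.2.1 estimates it "in patients of the CP with EoT response who fulfilled the following criteria": treatment completed, and either a value at 70 days or later or an earlier failure. SAP 4.1.2 defines relapse as negative at EoT and positive afterwards. Table 2 (SAP 4.2.2) sets the EoT window as "28 days prior to last dose - 7 days post last dose". The same section says that "all HCV RNA measurements will be performed at the sole discretion of the physician".

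**Missing values.** SAP 4.2.3 fills an empty window by flanking when both neighbouring values are negative. For EoT response and SVR, if the window is still empty but "there is an HCV RNA value after the window, then it will be imputed into the EoTR or SVR window respectively". Anything still missing counts as failure. These rules are introduced for RVR, EoT response and SVR; relapse is not named. The opening sentence, however, rules out imputation "except for the analyses of the HCV RNA endpoints and certain PRO endpoints". Protocol 9.7.1 assumes a negative EoT only if the succeeding value is negative, and otherwise defaults to failure.

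**SVR12 non-response categories.** Protocol 9.7.3.2 counts relapse from a negative value at EoT or, alternatively, at the last on-treatment measurement. SAP 4.1.2 and 4.2.7.2.1 start from EoT only; the latter requires a positive value "post-treatment and completed treatment as defined previously". Neither mentions the dropped alternative. The two SAP lists also differ: 4.2.7.2.1 adds death and a residual category for other insufficient virological response.

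**The concern.** A relapse rate needs an at-risk set fixed by status at the end of treatment, before the outcome is seen. If an empty EoT window is filled from the first post-treatment value, the outcome itself decides who is at risk. Patients who stay negative enter as non-relapsers, and relapsers already positive at that test drop out. Two programmers could also build different relapse tables from the present text.

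The category change matters separately. The non-response table is where a reader learns why patients failed. A completer suppressed on treatment and positive afterwards would be a relapse under the protocol, but with an empty EoT window the SAP can place that patient in a residual category. With 50-55 patients expected (SAP 3.2), one patient can be a visible share of all relapses.

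**Working it through.** **Figure to reproduce.** There is none. The documents give no expected relapse rate and no frequency of empty EoT windows, and the sample size has no statistical basis.

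**Step 1: SAP 4.2.3 applied to an empty EoT window.**

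| Last value before window | Next value negative | Next value positive | No later value |
|---|---|---|---|
| None | response (carried back) | non-response (carried back) | failure |
| Negative | response (flanking) | non-response (carried back) | failure |
| Positive | response (carried back) | non-response (carried back) | failure |

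Where there is a later value, it alone decides EoT status. That the next value is the one used is inferred: the SAP says only a value after the window, while flanking uses the closest values and the protocol says succeeding. Protocol 9.7.1 gives the same responders and non-responders, because a positive next value leaves EoT missing and so a failure.

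**Step 2: size on the imputed reading.** Assumed, not from the documents:
- r, the true relapse rate: 3% or 6%
- m, the share with an empty window, unrelated to relapse: 10-30%
- f, the share of relapsers already positive at the first later value: 0.5-1

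A fraction mf of relapsers leaves numerator and denominator, so the expected rate is r(1 − mf)/(1 − rmf).
- r = 6%, m = 10%, f = 0.5: 0.06 × 0.95/0.997 = 5.7%
- r = 6%, m = 30%, f = 1: 0.06 × 0.70/0.982 = 4.3%
- r = 3%, same two corners: 2.9% and 2.1%

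Expected relapsers lost = N·r·m·f. With N = 50 this is 0.15-0.9 (r = 6%) or 0.075-0.45 (r = 3%).

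Chance that at least one is lost = 1 − (1 − rmf)^N. With N = 50 and r = 6%, it runs from 1 − 0.997^50 = 14% to 1 − 0.982^50 = 60%. With r = 3% it is 7-36%.

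**Step 3: comparison with sampling error.** The Wilson 95% interval is [p + z²/2n ± z√(p(1−p)/n + z²/4n²)]/(1 + z²/n), with z = 1.96. For 3/50 the centre is (0.06 + 0.0384)/1.0768 = 0.0914 and the half-width 0.0708, giving 6.0% (2.1-16.2%). If one relapser is lost, 2/49 = 4.1% (1.1-13.7%). The shift of 1.9 points compares with an interval 14.1 points wide.

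**Step 4: is observed-only status clearly better?** Let empty windows occur in a share a of relapsers and b of cured patients, with true r = 6%. Observed-only gives r(1−a)/[r(1−a) + (1−r)(1−b)]; the imputed rule gives r(1−af)/[r(1−af) + 1−r].

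| a, b | Observed-only | Imputed, f = 1 | Imputed, f = 0.5 |
|---|---|---|---|
| 30%, 10% | 4.7% | 4.3% | 5.1% |
| 10%, 30% | 7.6% | 5.4% | 5.7% |

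Observed-only is further from 6% in three of the four comparisons. It is unbiased when gaps are unrelated to outcome, but not otherwise.

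**Step 5: the category change, which needs no assumption about imputation.** Take a completer who was negative at the last on-treatment test, has an empty EoT window and is positive at the first later test. Under protocol 9.7.3.2 this is a relapse. Under the SAP, EoT is either missing (observed reading) or positive (imputed reading), so it is not. In 4.2.7.2.1 the patient can fall into the residual insufficient-response category. In 4.1.2, which lacks that category, the patient can fall into the catch-all for missing SVR12 data or none of the other criteria, despite a measured positive value.

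**The case against.** The strongest objection is that SAP 4.2.3 limits its specific rules to RVR, EoT response and SVR. The relapse definition, the EoT window and the rule for counting a measurement as below 50 together supply an observed status. On that reading the at-risk asymmetry disappears. This stands: the imputed reading is possible, not established. The general opening phrase of 4.2.3 leaves it open. The Table 2 footnote on a window "added to consider possible relapse after day 210 in the analysis of the relapse rate" adds a time window and says nothing about imputation. The relapse table shell is in SAP Part II, which is not among the documents.

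A reader might infer that the SAP contradicts itself, because it admits a patient who "was a treatment failure between EoT and 70 days post-treatment". It does not: that clause is the alternative to a value at 70 days or later, and it applies in addition to EoT response and completion.

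A reader might also infer that every empty-window completer who relapses changes category. On the imputed reading, one who is first negative and later positive remains a relapse. Nor is the destination of the others certain: a positive value written into EoT might be taken as on-treatment failure.

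Admitting cured patients is not itself an error, since a negative post-treatment value is good evidence of EoT response. The fault would lie in treating relapsers differently.

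Empty windows may be few. SAP Table 1 schedules HCV RNA at EoT and at an early post-treatment visit, and the window is wide. At r = 1% the Step 2 formula gives only a 2.5-14% chance of losing a relapser among 50.

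**Conclusion.** The point holds as a minor one on a secondary endpoint. The SAP leaves EoT status in the relapse rate undefined. If it is imputed, the rate is biased downward whenever an empty-window relapser is already positive at the next value. The illustrative size (6% to 5.7-4.3%, 3% to 2.9-2.1%) rests wholly on assumed r, m and f and is small against the interval. The unannounced loss of the last on-treatment alternative stands whichever reading was meant. The SAP flags other departures from the protocol (4.1.1, the Table 2 footnotes, 4.2.8.4), so the silence here looks like an oversight.

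The documents do not support saying that the relapse rate will be biased, or that observed-only status is the one right definition. SVR12 is not touched: these patients remain SVR12 failures.

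**What to change.** 1. In SAP 4.1.2 and 4.2.7.2.1, restore the protocol's last on-treatment alternative in the relapse non-response category, and make the two category lists agree.
2. In 4.2.7.2.1, state that a positive post-treatment value is not carried back to EoT to define the relapse at-risk set. Say also that the default-to-failure rule does not remove such a patient, since protocol 9.7.1 shows that the default alone has the same effect.
3. Report the relapse rate twice: with EoT status observed in the window, and with the last on-treatment value used when the window is empty. Give the number of empty windows and those patients' SVR12 outcomes. Neither version need be declared the only correct one.

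The cost is a few sentences, one flag and one extra table, all on data already collected. The observed version loses patients: with 30% empty windows 50 become 35, and the Wilson interval widens from 14.1 points (3/50) to 17.0 points (2/35, 1.6-18.6%). It is also biased if gaps relate to outcome. The last on-treatment version uses a value from more than 28 days before the last dose, so it may count a late breakthrough as relapse. The reported relapse rate may come out slightly less favourable.
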